7.0 Study Intervention(s)/Investigational Agent(s)

7.1 Describe the study interventions (including behavioral interventions) and/or investigational agents (e.g., drugs or devices) to be used in this study. Consider each of the items listed below:

- *Drug/Device Handling: If the research involves drugs or devices, describe your plans to store, handle, and administer the drugs or devices so that they will be used only on subjects, and only by authorized investigators.*

PROTOCOL (STUDY) TITLE AND NUMBER

- *Describe whether any of the following will be used: microwaves, X-rays, DEXA scans, general anesthesia, or sedation*
- *If control of the drugs or devices used in this protocol will be accomplished by following an established, approved organizational SOP (e.g., Research Pharmacy SOP for the Control of Investigational Drugs, etc.), please reference the SOP in this section.*

Beverage Solutions:

This study will involve the use of 2 beverage solutions, which will be given to each participant. Beverages include citric acid, water, flavor, and either:

1. 0 kcal sucralose (to match the sweetness of the calorie-containing sugar beverage)
2. 75kcals sugars

Sucralose, sugars, and citric acid are common food and beverage additives that nearly every participant would have consumed previously in their normal diet.

The flavors used will be 0.002% acerola, 0.5% bilberry, 0.1% horchata, 0.1% lulo, 0.2% yuzu. 0.1% papaya, 0.1% chamomile, 0.1% aloe vera, 0.1% mamey, and 0.2% maqui berry (Bell Labs Flavors and Fragrances, IL, USA, product numbers: 33.81940, 15.80182, 132.81478, 141.14606. 101.29478, 102.82506, 141.31243, 141.31480, 46.29969 and 13.32059).

Foods:

This study will involve consumption of high carbohydrate (60% carbohydrate, 20% fat) and high fat (60% fat, 20% carbohydrate) test meals. In addition, a standardized diet (50% carbohydrate, 30% fat) will be provided for 2 days preceding each test meal measurement day. All of the foods included are typical foods nearly every participant would have consumed in their normal diet. Participants will be screened for food allergies/intolerances and excluded if any of these foods are included in the study diet or test meals.

Device Handling:

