8.0 Procedures Involved

8.1 *Describe and explain the study design:*

This is a crossover design and within-subjects analysis plan where participants receive all conditions during the flavor-nutrient conditioning paradigm of Aim 1. A subset of participants will also undergo fMRI scanning for Aim 1. All participants will undergo the controlled feeding diet and metabolic chamber measurements for Aim 2.

8.2 *Provide a description of:*

- *All research procedures being performed*
- *If the study has more than one procedure, session, and/or subject population, describe each procedure, session, and/or study population separately. For complex studies, you are encouraged to include a figure or chart.*

Study Overview:

Approximately 15 people from the general population will be recruited for Aim 1 (without fMRI) and Aim 2 of this randomized crossover design study conducted at FBRI. Of these 15 people, 5 will also undergo fMRI scanning as a part of Aim 1. This will be an approximately 6- to 7-week study. Participants will report to the research laboratory in Week 1 for the consent and training session. They will return to the research laboratory to complete 2 behavior sessions per beverage and a final post-testing session in Aim 1. Participants who are asked to complete the fMRI scan will undergo this measurement during the final post-testing session. For Aim 2, participants will report to the metabolic kitchen at FBRI for 2 days preceding each chamber measurement day to collect food to be consumed for each of those days. On each metabolic chamber measurement day, they will report to the metabolic chambers located in [name]. There will be a 5-day washout period between the first metabolic chamber session and controlled feeding for the second metabolic chamber session.

Recruitment and Screening:

Approved study recruitment materials will be distributed in the follow ways. Flyers will be posted on bulletin boards and approved posting sites throughout Roanoke, Blacksburg, and surrounding areas. Digital advertisements will be displayed on [name] lab and CHBR social media, VT News, and in list serves with permission.

PROTOCOL (STUDY) TITLE AND NUMBER

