Participants will come to the CHBR after a 4 hour fast. Participants will also be asked to abstain from moderate-to-vigorous physical activity for at least 24h prior to their session. This session will occur within the same week as Behavioral session 1 (or 3, as appropriate) with at least one day in between the sessions. They will first rate their internal states on standard scales.

Participants will then rest for approximately 30 minutes in preparation for the fasting indirect calorimetry measurement, which requires participants to be in a calm, restful state for accurate measurement. Participants will then undergo an indirect calorimetry measurement using a metabolic cart for approximately 30 minutes.

Indirect calorimetry determines gas exchange (i.e., oxygen consumption and carbon dioxide expiration) at the level of the lungs, and these measures are used to calculate energy expenditure and fat and carbohydrate utilization. During the test, participants lie supine while breathing normally into a transparent plastic hood. There are two holes on the hood, one that allows the inflow of room air into the hood, and another that allows for the extraction of gases into the gas analyzer via a vacuum tube (see picture below). The hood is then sealed around the participant's shoulders to prevent any gas from escaping during the test. Indirect calorimetry using a metabolic cart is a common, noninvasive assessment conducted routinely in both research and clinical nutrition practice. There is no more than minimal risk associated with this method of indirect calorimetry, and participants may wear normal clothes during the procedure. Since the hood is clear plastic, participants will be able to see and communicate with research personnel throughout the test. Should a participant become uncomfortable with the test, they may choose to stop the procedure at any time.

Following completion of the approximately 30-minute fasting indirect calorimetry measurement, participants will be given a 355 ml conditioning beverage (with the appropriate conditioning stimuli and flavor as determined during the consent and training session) to consume within 5 minutes. Participants will then rate their internal states on standard scales, and indirect calorimetry will be performed again for approximately 1 hour.

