AIM 2:

Controlled Feeding:

Participants will consume a standardized diet (50% carbohydrate, 30% fat) for 2 days prior to each metabolic chamber session. Total daily energy needs for each participant will be estimated using average resting energy expenditure determined during completion of Behavior Sessions 2 and 4 in Aim 1 and an activity factor derived from the physical activity questionnaire completed as part of the Consent and Training Session in Aim 1. The 2-day diet will be developed by a registered dietitian, and all foods will be prepared and assembled in the metabolic kitchen located in [name].

Participants will report to the metabolic kitchen to pick up coolers of food. Participants will be provided with all foods and drinks, except water, for the 2 days preceding each metabolic chamber measurement and instructed to consume all foods and beverages provided in the coolers.

Metabolic Chamber Sessions:

Participants will report to the metabolic chamber lab in [name] after a >8 hour (overnight) fast. Participants will also be asked to abstain from moderate-to-vigorous physical activity for at least 24h prior to their session.

Participants will then enter the flex metabolic chamber, which is outfitted with a bed, pillows, and a TV, to rest quietly during the fasting measurement. The fasting measurement will take approximately 50 minutes. After a fasting measurement, participants will be instructed to consume a high-carbohydrate (60% carbohydrate, 20% fat) or high-fat (60% fat, 20% carbohydrate) test meal within 5 minutes. Participants will then rest inside the chamber, without sleeping, for 5 hours during the post-consumption measurement.

The metabolic chamber operates under the same indirect calorimetry assumptions and principles as the metabolic cart, but the size of the chamber (4.6 cubic meters) allows for longer measurements with better comfort for participants compared with the metabolic cart. There are no known risks associated with this method of indirect calorimetry, and participants may wear normal clothes during the procedure. The chamber is outfitted with a 2-way intercom system, and one wall is clear plastic; participants will be able to see and communicate with research personnel throughout the test. Should a participant become

PROTOCOL (STUDY) TITLE AND NUMBER

uncomfortable with the test, they may choose to stop the procedure at any time. (See picture below.)

8.3 *Describe:*

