9.0 Data and Specimen Long Term Storage and Use

9.1 *If you will store data or specimens for future use, describe where you will store the data or specimens, how long they will be stored, and how and by whom the data or specimens will be accessed:*

Indirect calorimetry data and 24-hour food recall data will be stored on a secure network drive provided by FBRI. Behavioral (e.g., last time food eaten before measurement, last bout of exercise before measurement, etc.), anthropometric, responses to questionnaires, and pertinent energy expenditure variables collected during indirect calorimetry measurement will be stored in FBRI's instance of REDCap. Data will be stored indefinitely for future analysis and use in developing future protocols using indirect calorimetry methods. Only individuals with FBRI access to secure network drives and FBRI's instance of REDCap will have access to stored data. Plasma and/or serum aliquot samples will be frozen and stored for future analysis of insulin. As it is more cost effective to run an ELISA or Immulite 1000 with a full number of wells, these samples will be stored until they can be analyzed in batch. Additional aliquots of plasma and/or serum will be stored indefinitely after the completion of data analysis to allow for replicate testing to ensure data quality and for additional analyses as the field moves forward.

9.2 *For specimens, list the data to be stored or associated with each specimen:*

PROTOCOL (STUDY) TITLE AND NUMBER

Only a 4 digit number will be used to label data and the date collected.

9.3 *Describe the procedures to release data or specimens outside of the research team, including the process to request a release, approvals required for release, who can obtain data or specimens, and what data will be provided with specimens:*

No specimens will be released.

9.4 *Describe the identifiers to be included with stored data or specimens, as well as any key or code that could be used to make them identifiable. Describe where the code will be stored, who will have access to it, and when it will be destroyed:*

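### Aim 1 blood and cart sessions fix only a 4-hour fast; the previous meal and start time are not matched between a participant's sugar and sucralose sessions, which adds avoidable noise to primary-endpoint measures

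*Combined protocol and SAP*

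**What the plan says.** Section 8.2 gives the same preparation rule for the Aim 1 blood sessions (1 and 3) and cart sessions (2 and 4): "Participants will come to the CHBR after a 4 hour fast", plus 24 hours without moderate-to-vigorous activity. No previous meal, upper limit on the fast or start time is stated. The drink to be taken home before that evening's dinner implies only that a session ends before dinner.

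At a cart session, "Participants will then rest for approximately 30 minutes in preparation for the fasting indirect calorimetry measurement". That measurement lasts about 30 minutes. The drink follows within 5 minutes, and then "indirect calorimetry will be performed again for approximately 1 hour". The caloric drink holds "75kcals sugars" (section 7.1); the comparator holds none. Participants "complete 2 behavior sessions per beverage", one of each type, so each drink has one blood session and one cart session per person.

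Aim 2 also uses indirect calorimetry, but participants arrive "after a >8 hour (overnight) fast" after two days of standardized food. The Aim 2 diet is scaled from "average resting energy expenditure determined during completion of Behavior Sessions 2 and 4", that is, from the Aim 1 measurement.

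Section 9.1 lists "last time food eaten before measurement" among the stored variables and mentions 24-hour food recall without saying for which sessions. Section 5.2 names neither in a model. Section 4.1 lists blood metabolites and indirect calorimetry among the primary endpoints.

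**The concern.** Reading the rule as a minimum, a participant could comply by attending one cart session first thing in the morning after an overnight fast and the matching session 4 hours after a large lunch. The plan would call both baselines fasting. Four hours after a free-choice meal, energy expenditure, respiratory exchange ratio (RER), glucose and insulin may still carry some of that meal, and the remainder keeps falling while the drink response is recorded.

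The crossover removes stable differences between people. It does not remove differences between one person's sessions, and with one session of each type per drink nothing averages out within the person. With 15 completers and a 75 kcal stimulus, avoidable session-to-session noise counts. The same noise would weaken the section 5.2 regressions of liking on blood and energy expenditure measures if uncorrected values are the predictors.

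**Working it through.** **The plan's own figure.** The only sample-size arithmetic is in section 14.1: 15 completers with about 40% attrition gives 15/(1 − 0.40) = 25 to consent, which reproduces. The documents give no standard deviation, effect size, residual-meal figure or drink-effect figure, so everything below except the session timings and n = 15 rests on assumptions.

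**Timing at the minimum fast (section 8.2).** Baseline runs 4.5-5.0 h after the last food (4 h + 0.5 h rest, then 0.5 h measured). The post-drink hour runs about 5.1-6.1 h.

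**Assumed curve.** The share of a meal's thermic effect released by time t is F(t) = 1 − exp(−t/τ)(1 + t/τ). Energy released between times a and b is E × f × [F(b) − F(a)].

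- Previous meal: E = 300-900 kcal, f = 10%, τ = 0.75-2.0 h.
- Drink: E = 75 kcal, f = 5-10%, τ = 0.5-1.0 h, measured from 0.1 to 1.1 h.

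**Drink.** The total is 75 × 0.05 = 3.75 to 75 × 0.10 = 7.5 kcal. The measured hour captures 1.1-4.7 kcal.

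**Previous meal, one case in full (600 kcal, τ = 1.5 h).** The total thermic effect is 60 kcal.

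- Baseline: 60 × [F(5.0) − F(4.5)] = 60 × (0.8454 − 0.8009) = 2.67 kcal in half an hour, or 5.35 kcal/h.
- Post-drink hour: 60 × [F(6.1) − F(5.1)] = 60 × (0.9132 − 0.8532) = 3.60 kcal.
- Drift: 3.60 − 5.35 = −1.75 kcal.

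**Range at a 4 h fast.** Each cell shows baseline kcal/h; post-drink kcal; drift.

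| τ (h) | 300 kcal | 600 kcal | 900 kcal |
|---|---|---|---|
| 0.75 | 0.46; 0.18; −0.28 | 0.91; 0.36; −0.55 | 1.37; 0.54; −0.83 |
| 1.0 | 1.24; 0.64; −0.60 | 2.48; 1.28; −1.20 | 3.72; 1.91; −1.81 |
| 1.5 | 2.67; 1.80; −0.87 | 5.35; 3.60; −1.75 | 8.02; 5.40; −2.62 |
| 2.0 | 3.31; 2.56; −0.75 | 6.63; 5.12; −1.51 | 9.94; 7.68; −2.26 |

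For comparison, at 8 h (the lower bound of the Aim 2 fast) the same curves give 0.0-2.5 kcal/h at baseline, 0.0-1.8 kcal post-drink and a drift of 0.0 to −0.7 kcal.

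**What reaches the sugar-sucralose contrast.** After baseline subtraction, drift common to both sessions cancels and only the difference remains:

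- Both sessions at 4 h, same curve, 300 against 900 kcal: 0.83 − 0.28 = 0.55 kcal (τ = 0.75 h) up to 2.62 − 0.87 = 1.75 kcal (τ = 1.5 h).
- Same meal, one session at 4 h and the other at 12 h: 0.28 − 0.00 = 0.28 kcal (300 kcal, τ = 0.75 h) up to 2.62 − 0.04 = 2.58 kcal (900 kcal, τ = 1.5 h).
- Matched meal and timing, same curve: 0.

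**RER precision.** Assume a paired-difference SD of 0.03 from other sources and a last-meal SD per session of s = 0.01, 0.02 or 0.03.

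- Uncorrected values: SE factor √(1 + 2s²/0.03²) = 1.11, 1.37, 1.73; effective n = 15/factor² = 12.3, 7.9, 5.0.
- Change from baseline, with the 0.03 held fixed and correlation r between the meal effects at baseline and post-drink: effective n = 15/(1 + 4s²(1 − r)/0.03²). This is 14.4, 12.7, 10.7 for r = 0.9 and 13.2, 9.8, 6.8 for r = 0.7.

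**Resting value passed to Aim 2.** If the baseline residual of 0.5-9.9 kcal/h is scaled to a day, 0.5 × 24 = 12 and 9.9 × 24 ≈ 238 kcal/day, before the activity factor. A residual can only raise the value, so averaging two sessions does not remove it.

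**The case against.** The case for leaving the plan alone has real substance:

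- **Baseline.** Every session has its own pre-drink measurement, which removes much of the residual. This stands, with one gap: section 5.2 names change measures only for Aim 2 and never says Aim 1 values will be baseline-corrected.
- **Design.** Section 8.2 calls the study a randomized crossover, so previous-meal differences should fall on both drinks alike. This stands. A reader might infer a biased drink contrast, but that would need one drink's sessions to fall systematically at another time of day, and nothing in the documents says they do.
- **Size.** A reader might infer that the leftover meal is as large as the drink effect. That is one end of an assumed range and ignores the baseline; with a 300 kcal meal and τ = 0.75 h the residual is 0.18 kcal. A reader might likewise take effective n to be 12, 8 or 5. Those figures apply only without baseline correction and rest on SDs that are not in the plan. For glucose and insulin no size can be derived at all.
- **Purpose.** This is a feasibility pilot whose n was set by grant amount, expected feasibility needs and attrition, so there is no power target to miss. Section 5.2 also specifies no calorimetry contrast between drinks. Both points stand, but whether a 75 kcal signal can be measured is part of feasibility, and these measures are listed as primary endpoints.
- **Other controls.** Activity is restricted, special diets and recent weight change are exclusions, and failure to fast can lead to withdrawal. None of these fixes the previous meal or the hour.
- **Clock time.** It would be too strong to say that sessions may start at any hour. The start is unstated, and the pre-dinner drink bounds it.

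**Conclusion.** The point holds as a cheap improvement to precision, not as a flaw that invalidates Aim 1. What the documents establish is that preparation is looser in Aim 1 than in Aim 2, that nothing matches it between a participant's sugar and sucralose sessions, that each drink has one session of each type, and that the stored eating time has no stated use.

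The size is not established. On the assumed curves, baseline correction leaves a between-session difference of 0 to about 2.6 kcal, against a drink effect of 1.1-4.7 kcal in the measured hour. The upper end needs a large meal, a slow curve and unlike fasting times. The standard-error inflation of 11-73% for RER is for uncorrected values only and depends on the assumed SDs.

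The one place where a one-directional shift is plausible is the resting value used to scale the Aim 2 diet, because a residual meal effect can only raise it.

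**What to change.** In section 8.2, treat sessions 1 and 3 (blood) as one pair and sessions 2 and 4 (cart) as another. Book both sessions of a pair at the same clock time, within about 1 hour. Ask the participant to record the last meal before the first session of the pair and to repeat it, at the same time, before the second. This leaves the fast length as it is.

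In section 5.2, state that Aim 1 blood and calorimetry measures are analysed as change from the session's own pre-drink baseline. Add hours since last meal, derived from the eating time already stored, as a secondary or sensitivity covariate. It does not capture meal size and may vary little, so it supplements the matching and cannot replace it.

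Matching does not correct the level of the resting value passed to Aim 2. The differing pre-measurement conditions of the two aims should be reconciled, or the difference justified, where section 8.2 uses the Aim 1 value to set the Aim 2 diet.

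The cost is slightly less flexible booking, one more participant instruction and a few sentences in the analysis plan. No new staff, equipment or participants are needed.

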3.0 Background

3.1 Summarize the relevant prior research on this topic and gaps in current knowledge within the field of study:

There is conflicting evidence as to whether people with obesity find foods more reinforcing. People with obesity exhibit a greater motivation to consume palatable foods that does not habituate over time compared to healthy weight individuals (Saelens and Epstein 1996; Epstein et al. 2007; Temple et al. 2009); however, they do not report liking food more (Wall et al. 2020). Obesity is also associated with decreased sensitivity to post-ingestive signals (Beutler et al. 2020), possibly due to dietary history and exposure (Small and [name] 2019). Further, there is evidence for impaired reinforcement learning and habituation in studies from both humans with obesity and animals (Kroemer and Small 2016; Coppin et al. 2014; Reichelt, Morris, and Westbrook 2014; Johnson and Kenny 2010). Additionally, many hormones that are altered in states of obesity and metabolic dysfunction, such as insulin, influence food reinforcement. For example, a recent study in humans revealed central insulin signaling influences striatal dopamine tone (Kullmann et al. 2021). However, there is no experimental evidence in humans that post-ingestive learning is altered in states of obesity. The experiments in this proposal aim to fill that gap.

The normal process of energy metabolism involves a dynamic and coordinated switch between primarily fat and carbohydrate as oxidative fuel substrates, depending upon nutritional or physiological condition. This process of adjusting substrate oxidation to match substrate availability and energy demand is termed "metabolic flexibility" (Kelley and Mandarino 1990). Metabolic inflexibility, on the other hand, is caused by nutrient overload in the mitochondria and results in altered nutrient partitioning in which a consistent mix of oxidative substrates, regardless of nutritional or physiological

PROTOCOL (STUDY) TITLE AND NUMBER

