5.0 Study Design and Statistical Analysis Plan

5.1 *Describe the basic study design/approach (e.g., qualitative study using five focus groups of first year students to describe assimilation into the university community; randomized controlled trial of a behavioral change intervention to increase dietary intake of whole grains; pre- post-test evaluation of new pedagogical techniques to improve adult literacy):*

This study consists of two main aims. In the first aim, a within-subjects design will be used to compare the rewarding properties of two beverages, one containing 75kcal of sugar and one containing 0 kcal sucralose in individuals with normal weight and with excess adiposity or high body mass index. In a subset of participants, neural activation to each of the beverage tastes measured by fMRI will be compared. In the second aim, a within-subjects design will be used to compare metabolic response to a high-carbohydrate and high-fat test meal using a 6-hour metabolic chamber stay.

5.2 *Describe corresponding data analysis plan/approach (e.g., content analysis of focus group transcripts; descriptive analysis followed by linear regression modeling; nonparametric analysis of pre- and post-test measures):*

The first aim will use linear mixed effects models to compare ratings of the beverages and control for confounding variables. Linear regression will be used to relate blood and energy expenditure measures to liking and other subjective ratings. Standard preprocessing and statistical techniques for fMRI data will be used to compare beverages and look for relationships between neural activity and physiological measures. The second aim will use linear mixed effects models to compare energy expenditure and substrate oxidation to the test high-carbohydrate and high-fat meals measured in the metabolic chamber. Measures of metabolic flexibility will include changes in respiratory exchange ratio in response to each meal, the time to reach peak respiratory exchange ratio after meal consumption, slope from baseline to peak respiratory exchange ratio, and rate and slope of the return to baseline respiratory exchange ratio.

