At the end of this session, participants will be given 2 additional bottles containing 355 ml of the beverage consumed during this session. Participants will be instructed to consume one beverage 1 hour before dinner that evening and the other beverage 1 hour before lunch the following day. Participants will also be asked to complete a short survey regarding consumption of each of these beverages. An automated email containing links

PROTOCOL (STUDY) TITLE AND NUMBER

to a survey about the dinner and lunch beverage consumption will be sent using the same REDCap automated email function described above.

Post-Testing Session (for participants NOT undergoing fMRI portion of the protocol):
Participants will come to the CHBR after a 4 hour fast. Participants will also be asked to abstain from moderate-to-vigorous physical activity for at least 24h prior to their session. They will first rate their internal states on standard scales.

They will then taste and rate on standard scales the 2 flavors they consumed as part of the conditioning beverages throughout the protocol. After the rating, they will be given access to bottles containing the two they consumed during the protocol sessions and allowed to drink as much or as little as they want from the 2 bottles for 30 minutes. Consumed amounts of each beverage will be measured and recorded. Lastly, they will be offered 2 additional bottles containing the same conditioning beverages and allowed to choose one to take home with them in a forced-choice test.

Post-Testing Session (for participants who ARE undergoing fMRI portion of the protocol):

Participants completing the fMRI portion of the protocol will first report to the CHBR after a 4 hour fast. Participants will also be asked to abstain from moderate-to-vigorous physical activity for at least 24h prior to their session. They will first rate their internal states on standard scales. Then, they will be escorted to the Human Neuroimaging Laboratory in [name] for the fMRI scan.

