During this scan, participants will lie on a table that slides into the bore of the scanner. Using a head coil, the functional images will be acquired using an EPI bold sequence. Because the process is noisy (due to the sounds generated as the magnetic field gradients are changed), participants will wear a pair of headphones and disposable earplugs. During the entirety of the scan, subjects will be able to communicate with the experimenter via a speaker and microphone system. If subjects become uncomfortable or claustrophobic while in the scanner, they will be able to squeeze an emergency ball to get the attention of the experimenters who will then immediately remove them from the scanner. They can then withdraw from the study if they are unable to complete the MRI.

While in the magnet, subjects will taste small amounts of liquid stimuli that will be presented according to a standard paradigm we have successfully used before in taste MRI studies (Small et al., 2003; Small et al., 2004). In brief, hydraulic pumps will be used to pump solutions through plastic beverage tubing attached to a mouthpiece to the subject lying in the scanner. The mouthpiece will be sterilized and new beverage tubing will be used for each subject. The mouthpiece will be anchored to the head coil so that the end comfortably rests on the anterior tongue, just inside the subjects' mouth. This will not interfere with breathing through the mouth and subjects will always be able to breathe through their noses. To ensure participants can breathe through their nose, they will be asked to close their mouth and take one full breath (inhale and exhale) through their nose. If they are unable to breathe normally through their nose on the day of the scan, the scan will be rescheduled. The solutions will be dispensed through one tube at a time. The

PROTOCOL (STUDY) TITLE AND NUMBER

overall flow rate of solution into the mouth will be very slow (0.5ml of a liquid over 3-5 seconds). Each taste will be followed by a rinse of a tasteless solution.

After the fMRI is completed, they will be given access to bottles containing the two they consumed during the protocol sessions and allowed to drink as much or as little as they want from the 2 bottles for 30 minutes. Consumed amounts of each beverage will be measured and recorded. Lastly, they will be offered 2 additional bottles containing the same conditioning beverages and allowed to choose one to take home with them in a forced-choice test.

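### The post-test intake and take-home choice serve each flavor only in its own sugar or sucralose base, so they mix learned flavor preference with the drink's current energy and any residual taste difference

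*Combined protocol and SAP*

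**What the plan says.** The background (section 3.1) names the gap to be filled: "there is no experimental evidence in humans that post-ingestive learning is altered in states of obesity". Section 2.2 hypothesizes that reinforcement learning worsens as obesity increases. Section 4.1 lists drink preference and ratings among the primary endpoints.

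Section 5.1 describes the two drinks as "one containing 75kcal of sugar and one containing 0 kcal sucralose". Section 8.2 then sets out the post-test:

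- **Intake.** Participants are "given access to bottles containing the two they consumed during the protocol sessions" and may drink "as much or as little as they want from the 2 bottles for 30 minutes". The noun after the word two is missing, but the following sentences speak of beverages, so the original drinks are clearly meant.
- **Choice.** After that, "they will be offered 2 additional bottles containing the same conditioning beverages", and one is taken home. Here the stimulus is explicit.
- **fMRI subset.** The same two steps follow the scan: "After the fMRI is completed, they will be given access to bottles containing the two they consumed during the protocol sessions".
- **Ratings.** Participants who are not scanned also taste and rate the two flavors. The base in which these are served is not stated.

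The plan does guard against immediate taste differences. Sucralose is matched to the sugar drink for sweetness (7.1). The two flavors are chosen to be alike in liking and unfamiliarity, and a triangle test at training compares sugar- with sucralose-sweetened drinks (8.2). Participants who detect a difference are withdrawn (16.1), but that rule names maltodextrin, which section 7.1 lists in neither drink.

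**The concern.** Flavor-nutrient learning means that a flavor has gained value through what followed it during conditioning. To see that at post-test, the two flavors should differ only in their history. Here they also differ in what is in the bottle at the time. A preference for the sugar drink could then arise without learning, and an immediate effect in the other direction could hide learning.

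Section 8.2 describes no intake or choice test before conditioning that could be subtracted, and none in a common base. Section 5.2 gives no model for intake or choice and does not name the confounders to be controlled. For a pilot whose primary objective is the feasibility of measuring reward response after conditioning, whether these measures capture learning is a central question.

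**Working it through.** **1. What is crossed with what.**

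| Flavor | Base in conditioning | Base at post-test intake and choice |
|---|---|---|
| A | sugar | sugar |
| B | sucralose | sucralose |

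A minus B = (effect of history) + (effect of current base). Both terms have the same contrast in every participant, so no model fitted to these two measures can separate them. Varying which flavor gets which sweetener across participants would balance flavor identity but would leave history and base tied together.

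**2. Energy during the intake test.** Inputs: 75 kcal (7.1) and 355 ml (8.2). That the 75 kcal is per 355 ml bottle is an assumption; it is the natural reading but is not stated outright.

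- 75 / 355 = 0.211 kcal/ml for the sugar drink, against 0 for sucralose.
- 100 ml gives 21 kcal, 200 ml gives 42 kcal and 355 ml gives 75 kcal.

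The test lasts 30 minutes after a 4-hour fast. In the blood-draw sessions the protocol samples at 10, 15, 20 and 30 minutes after the drink, so it treats this window as relevant to the post-ingestive response.

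**3. Residual taste.** The triangle test has a chance rate of 1/3. Section 8.2 gives neither the number of trials nor a pass rule, so both are assumed here. For a participant who truly detects the difference half the time, the probability of a correct answer is 0.5 + 0.5 × 1/3 = 0.667.

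| Assumed rule | That participant is kept | A non-detector is flagged |
|---|---|---|
| 1 of 1 correct | 1 − 0.667 = 0.33 | 0.33 |
| 3 of 3 correct | 1 − 0.667³ = 0.70 | (1/3)³ = 0.04 |

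The test is described only at training. Each participant then receives 2 sessions × 3 bottles = 6 bottles of each drink before post-test.

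**4. Illustration for the choice.** The only sample-size figure that can be recomputed is the number to consent: 15 / (1 − 0.40) = 25, which agrees with section 14.1. With n = 15 completers, a two-sided exact binomial test at 5% needs at least 12 of 15 in one direction: 2 × P(X ≥ 12 | 0.5) = 2 × 0.0176 = 0.035 (11 of 15 gives 0.118). With no learning and an assumed share choosing sugar for immediate reasons:

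| Share choosing sugar | P(at least 12 in either direction) |
|---|---|
| 0.5 | 0.035 |
| 0.6 | 0.092 |
| 0.7 | 0.297 |

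Both the shares and the test are assumptions made for this illustration.

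**The case against.** The strongest reply has four parts.

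- **Taste is controlled.** A reader might infer that learning cannot be separated from immediate taste at all. The documents do not support that. If sweetness matching and the triangle test work as intended, completers can hardly tell the bases apart and the taste part is small. What remains is that the withdrawal rule and the test refer to different substances and no pass rule is given, so the control is not reliable as written. It covers taste only; nothing comparable covers energy.
- **The choice is made before that bottle is drunk.** This stands. Energy can affect the choice only by carry-over from the intake test just before it.
- **Both bottles are open together.** General satiation would lower intake from both. With total intake T and sugar share s, the difference is (2s − 1)T, so satiation shrinks the difference in ml but leaves the share unchanged. The direction and size of an energy effect therefore depend on the intake measure used, which section 5.2 does not define.
- **The stated comparison is between beverages.** Section 5.1 compares how rewarding the two drinks are, and using the original drinks fits that. The difficulty arises when the result is read as the learning in sections 2.2 and 3.1.

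A reader might also infer that the ratings already isolate flavor, or that they share the problem. Neither follows, because their base is unstated. For the in-scanner tastes, each delivery is 0.5 ml, so the energy argument hardly applies.

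**Conclusion.** The point holds for two measures. The take-home choice (explicitly) and the 30-minute intake (by clear reading) cannot, as designed, separate flavor history from the current base. For intake, the unguarded component is up to 75 kcal per full bottle, if that energy is per 355 ml. For taste, the confounding is reduced but not reliably removed.

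The size of the bias is unknown. The 9% to 30% range should not be read as this trial's false-positive rate: it depends on an assumed 60% to 70% sugar share and on a test the plan does not specify, applied to the measure on which energy acts only indirectly.

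Nor does it follow that the design would produce the hypothesized obesity result. A shift common to all participants does not by itself create a gradient. The bias would mimic impaired learning only if the immediate response varies with BMI, and the documents give no information on that. The change is worth making because it is cheap and the measures bear on the main hypothesis.

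**What to change.** Leave conditioning unchanged. At post-test, serve both conditioned flavors in one identical sweetness-matched base for the intake test and the forced choice, for example the existing 0 kcal sucralose base. Flavor history is then the only difference between the bottles, and section 5.2 can describe both as measures of learned flavor preference.

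In the same revision:

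- supply the missing noun in the two intake sentences of section 8.2;
- state the base used for the ratings and for the in-scanner tastes;
- reconcile the triangle test in section 8.2 with the withdrawal rule in section 16.1, and state the number of trials and the pass rule.

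If the original drinks are kept, section 5.2 should describe intake and choice as beverage preference and not as evidence of post-ingestive learning.

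The cost is one extra beverage preparation at post-test and some wording. The downside is that the sugar-paired flavor is tested in a base it was not trained with, and that preference for the drinks as consumed is no longer measured. If the bases are indistinguishable, as the plan intends, that mismatch is small.
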